 - o Hospital admission date;
 - ICU admission (if applicable);
 - Mobility;
 - o Respiratory parameters;
 - o Use of inotropic medication;
 - o RR/MAP;
 - Diagnostic interventions (X-ray of thorax, computerized tomography [CT] scans);
 - o Symptoms (fever, rash, abnormal cardiac function);
 - o Mechanical ventilation;
 - o Extracorporeal membrane oxygenation (ECMO).
- Infectious Disease Parameters:
 - Inflammatory markers;
 - Peripheral edema;
 - O Cytokine panel (full work-up pre- and post-treatment [serum]);
 - o Pre-treatment C-reactive protein (CRP) levels;
 - o Post-treatment CRP levels/24 h
 - Cardiac parameters/oxygen saturation;
- General Disease Parameters:
 - APACHE II score;
 - Performance status (Eastern Cooperative Oncology Group [ECOG]/Karnofsky);
 - o Laboratory assessments;
 - Virus titer;
 - o IL-6 status: pre-treatment serum IL-6 levels (ELISA or similar approach, e.g. multiplex cytokine array);
 - Extended blood panel (hemoglobin/hematocrit [Hb/Ht]), thrombocytes (including peripheral blood mononuclear cell [PMBC]);
 - Coagulation status;
 - o History of Human Immunodeficiency virus (HIV), Human herpes virus (HHV-8), hepatitis and tuberculosis infection.

	-
Inclusion Criteria	Patients must meet the following criteria to be eligible to participate in the study:
	1. Clinical and radiological diagnosis of pulmonary infection by COVID-19
	2. Positive microbiological evidence of SARS-CoV-2 infection
	3. Diagnosis of acute respiratory distress syndrome clinical panel in accordance with Berlin 2012 criteria
	4. For Cohort A only: subjects are eligible if they are enrolled and treated within 48 hours from the beginning of NIV or CPAP
	5. For Cohort B only: subjects are eligible if they are enrolled and treated within 48 hours from the beginning of invasive ventilation
Exclusion Criteria	Patients who meet the following criteria may NOT participate in the study.
	1. Active infection of bacterial or viral (non COVID-19) origin
Number of Patients	Up to 50 patients: 50% receiving treatment (Cohort A and Cohort B) and 50% matched case controls.
Countries/Number of Sites	1 site in Italy
Statistical Methods	All data will be summarized using descriptive statistical analyses as appropriate.
	All data will be presented in by-subject data listings.

PROTOCOL APPROVED BY PRINCIPAL INVESTIGATOR

Name / Title: [name] PhD

Address: [name]
Contact Info: UOC Ematologia

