8 OBSERVATIONAL PLAN

8.1 Overall Study Design and Plan – Description

This is a single-center, observational case control study in Italy that follows the use of treatment siltuximab in patients diagnosed with COVID-19 infection who have developed serious respiratory complications. Retrospective data collection will be carried out on patients who have received the drug through the compassionate use program. (this program is still ongoing, and enrolling patients).

Patients receiving siltuximab will be included into this observational study and will be divided into 2 cohorts, split in an approximate 3:1 ratio: 75% will be in Cohort A and are not in an ICU setting and are not on mechanical ventilation, while 25% will form Cohort B and consists of patients in an ICU setting who are receiving invasive ventilation.

[figure not shown]
Each patient will be matched to a consented case control receiving treatment other than siltuximab for their condition.

Match Criteria

Patients receiving siltuximab and controls will be matched according to the following criteria:

- Age (by decades)
- Sex (M/F)
- P/F fraction (<100, 100-150 or >150) at baseline
- Antiviral therapy

Figure 1: Study Design

Procedures outlined in this protocol are based on the compassionate use program, where patients are managed as per clinicians' best judgement and best practice. No procedures are required by this observational protocol. Data on the procedures already performed during the routine diagnosis and treatment of COVID-19 patients will be collected. The list of clinical and laboratory parameters is provided to direct data collection for this observational study (as available in the medical records).

During their hospitalization, patients will be monitored as per standard hospital practice or as per national (emergency) guidelines in accordance with extraordinary circumstances relating to the COVID-19 outbreak. After discharge, patients will be asked to provide (from their primary health care providers) relevant laboratory results for 30 days following start of COVID-19 treatment via ventilation (either mechanical or non-invasive).

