8.2 Justification of Study Design

The nature of the study allows for collecting information in a timely manner and will enable the researchers to generate hypotheses about the treatment under the compassionate use program for COVID-19. It is important to assess risk/benefit profile of siltuximab in this indication. A matched consented case control group (one case control per patient) has been included in this study to enable direct comparisons and to provide in-depth safety and efficacy data on siltuximab in the treatment of this patient population.

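### Controls are not matched on calendar time and concurrency is not clearly required, so period of admission may contribute to differences in the descriptive comparison

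*Protocol*

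**What the plan says.** Section 8.1 introduces its list with "Patients receiving siltuximab and controls will be matched according to the following criteria". Four items follow: age decade, sex, "P/F fraction (<100, 100-150 or >150) at baseline", and, last, "Antiviral therapy". The Synopsis gives the same four. Neither list contains an admission date, a ventilation start date or a study period.

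The control is defined in 8.1 as follows: "Each patient will be matched to a consented case control receiving treatment other than siltuximab for their condition". Section 11.1 takes in all siltuximab-treated patients and an equal number of consenting controls, without saying how to choose when several candidates qualify.

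The compassionate use programme is described as still recruiting, and data on treated patients are collected retrospectively (Synopsis, 8.1). Management is left to clinicians' judgement. Monitoring in hospital follows usual hospital practice or is "as per national (emergency) guidelines in accordance with extraordinary circumstances relating to the COVID-19 outbreak".

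Section 8.2 says that the control group "has been included in this study to enable direct comparisons". Section 11 plans a descriptive comparison of the two groups on the endpoints within each cohort, while 11.2.3 excludes statistical comparisons because the sample is small. The Synopsis data list includes "Hospital admission date", to be recorded if available. No use of that date in matching or analysis is stated.

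**The concern.** The primary endpoints in section 6 are invasive ventilation or 30-day death (Cohort A) and ICU stay or 30-day death (Cohort B). At one hospital, intubation and ICU stay plausibly depend on capacity, staffing and background treatment as well as on the patient, and these can shift during an outbreak. If treated patients and controls come from different parts of the study period, any such shift enters the difference between groups and looks like a drug effect. A wider confidence interval would not reveal it, because it moves the point estimate.

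The descriptive contrast could be read as evidence: 8.2 gives direct comparison as the reason for having controls, and 11.2.5 allows ad hoc results to be released in the public interest. Matching decides who becomes a control, and it is fixed in this protocol. With few pairs, later adjustment could do little if the two groups' periods barely overlapped.

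**Working it through.** **Is concurrency required anywhere?**

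- Match lists (Synopsis, 8.1): no calendar item.
- Section 9.1.1: enrolment and treatment must fall within 48 hours of the start of NIV or CPAP (Cohort A) or of invasive ventilation (Cohort B). This aligns time since ventilation. The word for enrolment hints at near-real-time recruitment.
- Section 10.1.2: describes informing an identified patient, with emergency consent if needed and a signature after viral clearance. This also hints at prospective identification.
- Against that, data collection on treated patients is retrospective, and 9.1.1 provides for data from deceased patients.

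Taken together, these sections suggest concurrent controls but do not require them.

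**Cohort sizes from the protocol's figures.** The enrolment figure of up to 50 is an estimate; 11.1 says that no sample size calculation was done, so there is no power figure to reproduce.

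- Treated: 50 × 50% = 25.
- Cohort A: 25 × 75% = 18.75, about 19 pairs.
- Cohort B: 25 × 25% = 6.25, about 6 pairs.

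**Illustration of period imbalance.** The protocol gives no event rates, so every risk and period share below is an assumption. With no drug effect, spurious risk difference (treated minus control) = (q_trt − q_ctrl) × (p_early − p_late), where q is the share of a group in the early period and p is the event risk in that period.

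| p_early → p_late | q_ctrl 0.75, q_trt 0.25 | q_ctrl 1, q_trt 0 | q_ctrl = q_trt |
|---|---|---|---|
| 0.50 → 0.40 | −0.50 × 0.10 = −0.05 | −0.10 | 0 |
| 0.50 → 0.30 | −0.50 × 0.20 = −0.10 | −0.20 | 0 |
| 0.60 → 0.30 | −0.50 × 0.30 = −0.15 | −0.30 | 0 |

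Exchanging the shares gives the same values with a positive sign. In Cohort A, a difference of 0.15 is 0.15 × 19 = 2.85, about 3 events.

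In terms of pairs, q_trt − q_ctrl is the share with treated early and control late, minus the share with the reverse. Only net discordance counts. With half the pairs discordant and a fall from 0.50 to 0.30, the bias has size 0.50 × 0.20 = 0.10 if all run one way, and (0.25 − 0.25) × 0.20 = 0 if they split evenly.

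**Scale against sampling error.** Unpaired 95% half-width = 1.96 × √(2p(1 − p)/n).

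- n = 19: 0.291 at p = 0.3; 0.318 at p = 0.5.
- n = 6: 0.519 at p = 0.3; 0.566 at p = 0.5.

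Partial imbalance (0.05 to 0.15) lies well inside these widths. Only complete separation combined with the largest assumed fall (0.30) reaches the Cohort A width.

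**The case against.** A reader might infer that emergency guidance changed during the study, or that controls will be historical. The protocol supports neither. It gives no study dates, accrual length or ICU load, and does not say that guidance changed; the reference to emergency guidelines sits in a sentence about monitoring. The consent process and the 48-hour rule lean towards controls identified in hospital at about the same time. This objection stands against any claim that the bias is present. It does not close the gap, because concurrency is left to inference.

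A reader might also infer a definite false benefit. The size rests wholly on assumed risks, the sign can go either way, and complete separation is hard to square with a continuing programme at one site.

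The study is exploratory and hypothesis-generating, and 11.2.3 rules out formal comparisons. Subject listings would also show date imbalance if dates are recorded. That limits the harm, but the descriptive contrast in section 11 remains exposed. Matching on antiviral therapy may partly track treatment period, and the single site removes between-centre differences; neither replaces matching on date.

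The strongest objection concerns the remedy. A hard date window would be arbitrary and could leave treated patients unmatched, especially in Cohort B. Treatment also followed physicians' decisions (13.1, 13.2), so untreated patients from the same days may be those whom clinicians chose not to treat. Closer dates can therefore exchange some period bias for selection by indication. Both points stand and shape the fix.

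**Conclusion.** The point holds as a modest design gap. Calendar time is absent from both match lists and no section clearly requires concurrent controls, so period of admission may contribute to differences in intubation, ICU stay or death. Direction and size cannot be determined from the protocol, and the bias is zero if the groups are balanced over time. Under the assumed risks, partial imbalance gives 5 to 15 points in either direction and complete separation 10 to 30 points, against a sampling half-width of 29 to 32 points in Cohort A and 52 to 57 in Cohort B. The documents do not support saying that the comparison is biased, or that it favours siltuximab. The case for changing the text is that the improvement is cheap and has to be made where controls are chosen.

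**What to change.** Add to the match criteria in the Synopsis and 8.1, for example: *Among candidates who meet all four criteria, the control is the patient whose qualifying ventilation (NIV or CPAP in Cohort A, invasive ventilation in Cohort B) started nearest in calendar date to that of the treated patient. No pair is dropped because of the date gap. The gap is reported for each pair and start dates are tabulated by group; pairs far apart in time are flagged.*

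No new data item should be needed. Ventilation start must be known to apply the 48-hour rule and to begin the 30-day record, and admission date is already on the data list.

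The cost is slightly more work in selecting controls. Some pairs may still be distant in date, particularly among the roughly 6 in Cohort B. Date matching does not remove selection by indication, so that limitation should be stated alongside the results.

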8.2 Justification of Study Design

The nature of the study allows for collecting information in a timely manner and will enable the researchers to generate hypotheses about the treatment under the compassionate use program for COVID-19. It is important to assess risk/benefit profile of siltuximab in this indication. A matched consented case control group (one case control per patient) has been included in this study to enable direct comparisons and to provide in-depth safety and efficacy data on siltuximab in the treatment of this patient population.

9 STUDY POPULATIONS

9.1 Eligibility

9.1.1 Inclusion Criteria

Patients must meet the following criteria to be eligible to participate in the study:

- 1. Clinical and radiological diagnosis of pulmonary infection by COVID-19
- 2. Positive microbiological evidence of SARS-CoV-2 infection
- 3. Diagnosis of acute respiratory distress syndrome clinical panel in accordance with Berlin 2012 criteria
- 4. For Cohort A only: subjects are eligible if they are enrolled and treated within 48 hours from the beginning of NIV or CPAP
- 5. For Cohort B only: subjects are eligible if they are enrolled and treated within 48 hours from the beginning of invasive ventilation

While approving this protocol, it is understood that the RA/IEC have approved collection and analysis of the data from deceased patients with COVID-19. See also protocol section 10.1.2.

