6 STUDY OBJECTIVES

The is a case control study to observe treatment and collect data on two cohorts of patients treated with siltuximab and a corresponding case control group of patients who have developed severe respiratory complications with COVID-19 infection.

Primary objective

Cohort A: reduction of the need of invasive ventilation or 30-day mortality

Cohort B: reduction of mortality

Secondary objectives

Cohort A

Reduction of the need of time of ventilatory support

Improvement of the lung function

Improvement of radiologic findings

Cohort B

Reduction of days of need of intubation

Percentage of patients that undergo to tracheostomy

Improvement of the lung function

Improvement of radiologic findings

Primary endpoint:

Cohort A: Reduction of the rate of need of invasive ventilation or 30-day mortality

Cohort B: Reduction of length of ICU staying or 30-day mortality

Secondary endpoints:

Cohort A

Reduction of days of need of ventilatory support

Improvement of P/F fraction (resolution of ARDS i.e. P/F>300, or increase from baseline value of at least 50% if P/F>100 or 100% if P/F<100, at day 3, 8 and 15)

Reduction of the duration of invasive ventilation or length of ICU

Improvement of radiologic imaging

Cohort B

Reduction of days of need of intubation

Percentage of patients that undergo to tracheostomy

Improvement of P/F fraction (resolution of ARDS i.e. P/F>300, or increase from baseline value of at least 50% if P/F >100 or 100% if P/F<100, at day 3, 8 and 15)

Improvement of radiologic imaging

Exploratory end points

Correlation of outcomes with IL-6 levels

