10.1.1 Tabulated Overview

All available data will be captured from medical records. The following data will be recorded (if available):

Laboratory-confirmed COVID-19 (Positive, validated RT-PCR Assay of nasopharyngeal swabs and ideally serum)

Demographics
Prior medications used

Past Medical History

The following data will be recorded from the time of first ventilation for 30 days (if available):

General Information	
Hospital admission	
ICU admission	
Mobility	
Respiratory parameters	
Use of inotropic medication	
RR/MAP	
Rx (X-Thorax, CT scans)	
Fever/rash/abnormal cardiac function	
Mechanical ventilation	
ECMO	
Infectious Disease Parameters	
Inflammatory markers	
Peripheral edema	
Cytokine panel- Full Cytokine panel workup pre and post treatment (Serum)	
Pre-treatment CRP Levels	
Post-treatment CRP Levels /24h	
Cardiac parameters/Oxygen saturation	
General Disease Parameters	
APACHE II score	
Performance status (ECOG/Karnofsky)	

Laboratory Assessments

Virus titer

IL-6 status Pre-treatment Serum IL-6 levels (ELISA or similar approach, e.g.: Multiplex cytokine array)

Extended blood panel (Hb/Ht), thrombocytes, including PMBC

Coagulation status

History of HIV/HHV-8/Hepatitis/Tuberculosis infections

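### The stated 30-day window runs from first ventilation, siltuximab may follow up to 48 hours later, and controls have no matching index time, so pre-infusion deaths and Cohort A intubations can count only against controls

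*Protocol*

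**What the plan says.** **Time window.** Section 10.1.1 of the protocol states: "The following data will be recorded from the time of first ventilation for 30 days (if available". The Synopsis sets the same window. For discharged patients, Section 8.1 asks for "relevant laboratory results for 30 days following start of COVID-19 treatment via ventilation (either mechanical or non-invasive".

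**Entry of treated patients.** Section 9.1.1 gives one rule per cohort: "For Cohort A only: subjects are eligible if they are enrolled and treated within 48 hours from the beginning of NIV or CPAP" and "For Cohort B only: subjects are eligible if they are enrolled and treated within 48 hours from the beginning of invasive ventilation". Of the treated patients, Section 8.1 says "75% will be in Cohort A and are not in an ICU setting and are not on mechanical ventilation".

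**Controls.** Section 8.1: "Each patient will be matched to a consented case control receiving treatment other than siltuximab for their condition". The match criteria are age decade, sex, baseline P/F band and antiviral therapy. Elapsed time on ventilation and event status are not among them.

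**Primary endpoints (Section 6).** "Cohort A: Reduction of the rate of need of invasive ventilation or 30-day mortality" and "Cohort B: Reduction of length of ICU staying or 30-day mortality". Neither says what day 0 is. Baseline and the origin of days 3, 8 and 15 in the P/F endpoint are not defined either.

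**Use of the controls.** Section 8.2 says they are included so that the groups can be compared directly. Section 11 plans a descriptive comparison within each cohort. Section 11.2.3 rules out statistical comparisons between the groups.

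**The concern.** A treated patient is recognised as treated only at infusion. Until then that patient must have survived and, to be in Cohort A, must not have been intubated. If follow-up is counted from first ventilation, the wait is event-free by construction in the treated group. A control has no infusion, so treatment within 48 hours can only mean other care, which may begin together with ventilation. It imposes no equal wait.

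Take two Cohort A candidates with the same course, both intubated at hour 6. The control contributes a primary event. The other, whose infusion would have come at hour 30, never enters the Cohort A treated group. Groups with identical prognosis would then show different rates of death and intubation with no drug effect at all.

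Baseline P/F is a match variable and days 3, 8 and 15 are assessment times, so without a common origin these too may refer to different stages of illness in the two groups.

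**Working it through.** The protocol gives no event rate, event timing or sample-size calculation, so there is no stated figure to reproduce. The bias can only be sized under assumptions.

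**From the protocol**
- Delay from start of support to infusion: 0 to 48 h (Section 9.1.1).
- Recorded window: 30 days from first ventilation (Section 10.1.1). The delay is at most 2/30 = 6.7% of it.
- Size: up to 50 patients, half treated, split about 3:1. That is 50 × 0.5 = 25 per group, with 25 × 0.75 = 18.75 (about 19) in Cohort A and 25 × 0.25 = 6.25 (about 6) in Cohort B.

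**Assumed**
- No drug effect.
- 30-day event risk from first ventilation R = 50%.
- Infusion times uniform over 0 to 48 h and unrelated to prognosis.

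**Formula.** Let F(u) be the risk of an event by time u, and m its mean over the infusion times. Controls show R. Treated patients, who must be event-free at infusion, show (R − m)/(1 − m).

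**Constant hazard**
- Rate = ln 2/30 = 0.0231 per day, so F(48 h) = 1 − 0.5^(2/30) = 4.5%.
- m = 1 − (1 − e^(−0.0462))/0.0462 = 0.0227.
- Treated risk = (0.50 − 0.0227)/(1 − 0.0227) = 48.8%, a spurious reduction of about 1.2 points.

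**Front-loaded events** (F linear within 48 h, so m = F(48 h)/2)

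| F(48 h) | m | Treated risk | Spurious reduction |
|---|---|---|---|
| 10% | 0.05 | 0.45/0.95 = 47.4% | 2.6 points |
| 20% | 0.10 | 0.40/0.90 = 44.4% | 5.6 points |
| 30% | 0.15 | 0.35/0.85 = 41.2% | 8.8 points |

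With R = 50%, these rows put 20%, 40% and 60% of all 30-day events into the first 2 days.

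**In patients.** With 19 per group in Cohort A, 1.2 points is 0.012 × 19 = 0.2 of an event and 8.8 points is 0.088 × 19 = 1.7 events.

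**Simulation with other risks** (uniform infusion times, R = 30%, 50% and 70%). The spurious reduction is 0.8, 1.2 and 1.2 points with a constant hazard. With a front-loaded Weibull hazard (shape 0.5) it is 4.4, 6.3 and 6.8 points. When controls must be event-free at their match's infusion time and both clocks start there, the difference is at most 0.2 points in every scenario.

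**Length of follow-up.** Days recorded after infusion = 30 − delay. Infusion at 48 h leaves 30 − 2 = 28 days. In Cohort B, k days of NIV before intubation leave 28 − k.

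**The case against.** **The endpoints name no origin.** This is correct. The ventilation origin belongs to data recording and to post-discharge laboratory results. A reader might infer that the protocol expressly starts the mortality clock there, but it does not; that is only the natural reading of the one window given. The alternative does not remove the problem. If treated patients are counted from infusion and controls from ventilation, the simulated gap vanishes under a constant hazard. Under the front-loaded hazard it remains 30.0 − 26.0 = 4.0, 50.0 − 44.4 = 5.6 and 70.0 − 63.9 = 6.1 points, and the recorded data end too early.

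**The analysis plan may settle the origin.** It may, but eligibility, control selection and the data window are fixed in the protocol. An analysis plan cannot recover days that were never collected.

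**The study is exploratory.** Sections 8.2, 11.2 and 11.2.3 support this, and it limits the consequences. The descriptive comparison remains, however, and leaving out a test does not remove bias from it.

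**Consent may select surviving controls.** This could offset part of the bias. Physician emergency consent (Section 10.1.2) and the inclusion of deceased patients (Section 9.1.1) limit it.

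**Stronger readings that the protocol does not support**
- *Both primary endpoints favour siltuximab.* Early control deaths shorten ICU stay, so the direction for that part of the Cohort B endpoint is unclear.
- *NIV before intubation lengthens the immortal period in Cohort B.* Cohort B patients in both groups have survived it to reach intubation. The differential gap stays at 48 h or less.
- *All early events count only for controls.* Only events before infusion are lost. A patient infused at hour 2 and intubated at hour 20 is a siltuximab event.
- *Retrospective patients cannot have been enrolled within 48 hours.* The word may refer to the compassionate use programme, which was still enrolling.
- *The bias could exceed 20 points.* With every infusion at 48 h and F(48 h) = 30%, the treated risk is 0.20/0.70 = 28.6%, a gap of 21.4 points. That is an extreme bound, not an expected size.

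**Conclusion.** The point holds for deaths in both cohorts and for intubation in Cohort A. Followed as written, the plan lets these events count for controls, but not for siltuximab patients, during the wait for infusion. The descriptive comparison is biased towards siltuximab on those components.

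The size is uncertain because event timing is unknown. At a 50% risk with uniform infusion times it runs from about 1.2 points (constant hazard) to between 2.6 and 8.8 points (10% to 30% of patients with the event by 48 h). The low end is negligible in a group of 19. The high end is nearly two patients, enough to colour a descriptive result.

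Two related defects do not depend on these assumptions: time zero is undefined for the endpoints, baseline and visit days, and the recorded window ends before 30 days after any delayed infusion.

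**What to change.** 1. Define one index time. For treated patients it is the infusion. For each matched control it is the same elapsed time since the start of the cohort-defining support (NIV or CPAP in Cohort A, invasive ventilation in Cohort B).
2. Require each control to be alive at that index and, in Cohort A, not intubated. Controls remain patients on treatment other than siltuximab, as Section 8.1 defines them.
3. Count baseline P/F, days 3, 8 and 15, and all 30-day outcomes from the index in both groups. Say so in Section 6 and in the match criteria.
4. Extend data collection in the Synopsis and Sections 8.1 and 10.1.1 to 30 days after the index.
5. State how inclusion criteria 4 and 5 apply to controls, and whether enrolment there means the compassionate use programme or this study.

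The cost is protocol and CRF wording, plus start times of support and infusion taken from the charts. A few controls with very early events would be replaced, and the apparent effect may become less favourable to siltuximab.
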